7.7 LOST TO FOLLOW-UP

Some actively enrolled subjects may not return for follow-up exams due to a variety of reasons. Study personnel must make reasonable efforts to contact the subject and document the following contact attempts prior to declaring a subject to be lost to follow-up (LTFU): the subject has been contacted according to the site's policies, but no less than 2 documented phone contacts and 1 certified letter without response. Copies of all attempts to reach the subjects per regular mail or email and/or the attempts to contact the subject via other means should be documented and that documentation should be kept with the subject's source documents at site. A subject will be considered LTFU if he/she does not appear for the scheduled study visit for 2 consecutive visits and does not return for a final visit, and study personnel are unable to contact the subject.

7.8 WITHDRAWAL

7.8.1 Withdrawal from Treatment

Subjects may be withdrawn from having the study device implanted at a date close to surgery or during surgery for the following reasons:

- At the discretion of the Investigator due to:
 - A change in treatment being clinically warranted
 - An adverse event
 - Any other significant reason identified by the Investigator.

If at any point during the study, the study device needs to be revised for any reason intraoperative data from the reoperation will be collected according to the Reoperation Case Report Form (CRF).

Reoperation cases will not be enrolled into the revision repair subject group if the subjects has been randomized previously into the ARCR augmented with REGENETEN arm. However subjects that have been randomized into the ARCR alone arm can be enrolled into the Revision Repair subject group.

CONFIDENTIAL AND PROPRIETARY

Study Protocol	Smith-Nephew
A Prospective, Multi-center, Randomized Controlled	Number:
Study to Evaluate the Safety and Efficacy of ARCR	REGENETEN.2020.01
augmented with REGENETEN™ Bioinductive Implant	Version: 2, 08 Dec 2021
System in Full-thickness Tears (large or massive) Repair versus ARCR alone	Page: 43 of 134

Following reoperation subjects shall continue to have follow-up visits in order to monitor the subject's health status only. Potential data following the reoperation will not be included as study data but presented separately as safety data.

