7.6 ENROLLMENT

Every subject that has signed consent, met inclusion/exclusion criteria, and received either ARCR augmented with REGENETEN or ARCR alone will be considered enrolled in the study.

In the event that a subject has a sequential bilateral ARCR augmented with REGENETEN or ARCR alone, both shoulders treated after informed consent can be enrolled in the study.

A subject that has been randomized into the ARCR augmented with REGENETEN arm and with a diagnosis of a recurrent large or massive tear will not be enrolled into the revision repair subject group. However subjects that were randomized into the ARCR alone arm can be enrolled into the revision repair subject group in case of recurrent large or massive tears.

Subjects that provided informed consent but do not receive the study treatment for any reason will be considered as screen failure.

CONFIDENTIAL AND PROPRIETARY

Study Protocol	Smith-Nephew
A Prospective, Multi-center, Randomized Controlled	Number:
Study to Evaluate the Safety and Efficacy of ARCR	REGENETEN.2020.01
augmented with REGENETEN™ Bioinductive Implant	Version: 2, 08 Dec 2021
System in Full-thickness Tears (large or massive) Repair versus ARCR alone	Page: 42 of 134

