8.3.4 Safety Endpoints

Safety endpoints include the collection of the following events:

- All adverse events (AEs) occurring from the time of subject enrollment until study termination or study completion including intra-operative adverse events,
- Device Deficiencies.

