9.1.3 Operation – Visit 2 (Day 0)

- 1. Query subject regarding any changes in general health and the use of concomitant medications (e.g. oral or injected steroid use in last 4 weeks).
- 2. Confirm eligibility based on arthroscopic visualization of the tear and confirm size using a calibrated probe.
- 3. Assign the Randomization ID per randomization schedule. Screen Failure subjects should not be assigned randomization numbers, but their demographic information must be captured in the appropriate CRF with the reason for screen failure specified.
- 4. Commence operation as per the randomization schedule.
- 5. Collect operative and discharge data (including implant information) according to the CRF.
- 6. If any AEs, ADEs or DD are observed or reported, they must be recorded as instructed in Section 12 Adverse Events and Device Deficiencies.
- 7. Instruct the subject on proper postoperative care/procedures as per standard of care and/or Sponsor's recommendation given in section 6.2 Product Use.
- 8. Instruct the subject to document Opioid Use over the next 2 weeks on a daily basis.
- 9. Instruct the subject on follow-up procedures, including returning the treatment facility for follow-up at Visit 3 in 14 (± 5) days.

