10.2 ANALYSIS POPULATIONS

The following study populations and analysis sets will be defined.

- Full analysis set (FAS): following the Intention to Treat principle including all randomized patients who were recruited into the study and attended at least one post-surgery assessment. This analysis population includes all randomized patients in the groups to which they were randomly assigned, regardless of their adherence with the entry criteria, regardless of the treatment they actually received, and regardless of subsequent withdrawal from treatment or deviation from the protocol.
- Per protocol set (PP): including all patients in the full analysis set who have no significant protocol deviations and met the inclusion/exclusion criteria.
- Safety analysis set (SAF): including all patients who have received the study device.

CONFIDENTIAL AND PROPRIETARY

Study Protocol	Smith-Nephew
A Prospective, Multi-center, Randomized Controlled	Number:
Study to Evaluate the Safety and Efficacy of ARCR	REGENETEN.2020.01
augmented with REGENETEN™ Bioinductive Implant	Version: 2.0, 08 Dec
System in Full-thickness Tears (large or massive) Repair	2021
	Page: 71 of 134

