10.5 SAFETY ANALYSES

All safety endpoints will be summarized using the safety population.

Adverse Events

The number of subjects reporting: adverse events, serious adverse events, adverse device effects, serious adverse device effects, and unanticipated serious device effects will be summarized. In addition, for each adverse event, the following will be summarized: severity, the relationship to investigational device use, outcome and duration of the resolved adverse events and the duration of the adverse events at trial discontinuation.

Device deficiencies

The number of device deficiencies and the number of patients reporting a device deficiency will be summarized as well as a summary of device deficiencies with the potential to cause SADE.

Additional summaries of safety endpoints, if applicable, will be described in the SAP.

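### On a plain reading of the safety set, subjects whose REGENETEN implantation is attempted but abandoned are left out of the planned safety summaries, although their events are still recorded.

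*Combined protocol and SAP*

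**What the plan says.** Section 7.8.1 provides for implantation to be called off: "Subjects may be withdrawn from having the study device implanted at a date close to surgery or during surgery for the following reasons". The reasons are at the investigator's discretion: a clinically warranted change of treatment, an adverse event, or any other significant reason.

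Section 10.2 defines the set used for safety: "Safety analysis set (SAF): including all patients who have received the study device". It does not say what counts as having received the device. Section 10.5 then states: "All safety endpoints will be summarized using the safety population". The same section covers deficiencies: "The number of device deficiencies and the number of patients reporting a device deficiency will be summarized".

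The safety endpoints are broader than that set. Section 8.3.4 lists device deficiencies and also: "All adverse events (AEs) occurring from the time of subject enrollment until study termination or study completion including intra-operative adverse events". On the day of operation, Section 9.1.3 (item 6) instructs: "If any AEs, ADEs or DD are observed or reported, they must be recorded as instructed in" Section 12, and Section 12.3 sends events of any kind and deficiencies to the eCRF.

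**The concern.** The safety set is conditioned on something that the safety outcome can determine. If an anchor fails to deploy, tissue is damaged or a component malfunctions, and the surgeon then stops, that problem is the reason the subject never ends up with the device. A set limited to recipients removes the subject and, with the subject, the event.

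The protocol treats such events as part of what it wants to measure. Section 12.1.2 counts adverse events arising from deployment, implantation or malfunction as adverse device effects. Section 12.1.6 counts malfunctions and use errors as deficiencies. The warnings in Section 4.4.4 foresee damage to tissue, implant or anchor during anchor deployment.

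At stake are the adverse-event and deficiency tables of a trial that, according to the synopsis and Section 8.1, is to support registration in China, where Section 6.3.1 describes the device as investigational.

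**Working it through.** The plan states no figure on this point, so the check is first a comparison of text and then an illustration.

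**Text, step by step**

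1. Section 7.8.1: implantation can be stopped during surgery, and an adverse event is one permitted reason.
2. Section 10.2: membership of the safety set requires having received the device. A subject left with nothing implanted does not meet that on the plain reading.
3. Section 10.5: adverse events and deficiencies are summarised on that set. The full analysis set keeps subjects whatever treatment they received, but no safety analysis is assigned to it.
4. No section returns attempted but abandoned implantations to the safety set or plans a separate summary for them. Section 7.8.2 keeps data up to withdrawal, but it concerns withdrawal from the study, not from treatment, and does not alter the safety set.
5. Section 9.1.3 (item 6) and Section 12.3: the event is recorded. Serious events, and deficiencies that could have led to a serious device effect, reach the sponsor within 24 hours.

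The data therefore exist, but the planned tables do not include them.

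**Illustration**

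From the documents: 130 subjects planned in the randomised device arm (Section 11). Assumed, because the documents give no values: *k* abandoned implantations, *x* of them with an event or deficiency, and *m* subjects with an event among completed implantations.

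- Written safety set: *m* / (130 − *k*)
- Set of attempted implantations: (*m* + *x*) / 130

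With *x* = *k*, so that every abandoned case carries an event:

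| *m* | *k* | Written set | Attempted set | Relative shortfall |
|---|---|---|---|---|
| 0 | 1 | 0/129 = 0% | 1/130 = 0.8% | 100% |
| 0 | 3 | 0/127 = 0% | 3/130 = 2.3% | 100% |
| 0 | 7 | 0/123 = 0% | 7/130 = 5.4% | 100% |
| 5 | 1 | 5/129 = 3.9% | 6/130 = 4.6% | 16% |
| 5 | 3 | 5/127 = 3.9% | 8/130 = 6.2% | 36% |
| 5 | 7 | 5/123 = 4.1% | 12/130 = 9.2% | 56% |
| 20 | 2 | 20/128 = 15.6% | 22/130 = 16.9% | 8% |
| 20 | 4 | 20/126 = 15.9% | 24/130 = 18.5% | 14% |

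For *m* = 0, the exact (Clopper-Pearson) 95% upper limits on the written set are 2.8%, 2.9% and 3.0%. On the attempted set the intervals are 0.02% to 4.2%, 0.5% to 6.6% and 2.2% to 10.8%.

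The direction also rests on an assumption. The written set understates the rate when *x*/*k* exceeds *m*/(130 − *k*), that is, when events are more frequent in abandoned than in completed cases. If abandoned cases carried no events (*x* = 0, *k* = 3, *m* = 5), the written set would give 5/127 = 3.9% against 5/130 = 3.8%, a slight overstatement. With *k* = 0 the two sets coincide. Section 10.5 plans numbers of deficiencies and of patients, not rates; in those counts the loss is simply whatever occurred in the abandoned cases.

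**The case against.** The strongest reply has four parts.

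**Nothing is lost from collection.** This is correct. A reader might infer from Section 7.6 ("Subjects that provided informed consent but do not receive the study treatment for any reason will be considered as screen failure") and from Section 9.1.3 ("their demographic information must be captured in the appropriate CRF with the reason for screen failure specified") that an abandoned case becomes a screen failure with only demographics on file, and that Section 8.3.4 then never counts its events. The documents do not support that. The screen-failure wording in Section 9.1.3 belongs to the randomisation step and does not limit collection to demographics; the later item on recording events follows it. The amendment rationale (Section 21.1.2) says the flowchart now places randomisation after the repair. A randomised subject whose implantation is then abandoned has therefore already had ARCR, and arguably meets the enrolment definition in Section 7.6.

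**Partial use may count as receipt.** The product is a system of instruments, scaffold and anchors, and the term is undefined, so a subject in whom some component was used might be classed as a recipient. This stands as a limit: the exclusion follows from the plain reading, not from an explicit rule about abandoned cases. It also means that two analysts could classify the same subject differently.

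**Not every withdrawal is device-related.** Section 7.8.1 also covers decisions before surgery and reasons unconnected with the device. A component that fails in an implantation that is then completed stays in the set. The concern is confined to implantations attempted and then abandoned.

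**The SAP may settle it.** Section 10 is only a brief description, and Section 10.5 leaves further safety summaries to the SAP where applicable. None is specified in the text available, so this reply cannot be relied on.

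A further inference would be that such events will appear in the control column. No as-treated safety table is specified, so that does not follow.

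**Conclusion.** The point holds for the tabulated safety results. Read plainly, Sections 7.8.1, 10.2 and 10.5 together omit attempted but abandoned implantations from the adverse-event and deficiency summaries, and no other section restores them. The exclusion can depend on the event being measured, so the device summaries can be biased in the device's favour.

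The size cannot be estimated, because the documents give neither an abandonment rate nor an event rate. The illustration ranges from no effect, when nothing is abandoned, to complete omission of the events concerned, when they occur only in abandoned cases. A reader might be tempted to quote a fixed shortfall such as one third or one half. Any such figure is set by the assumed counts and has no basis in the documents. The conclusion rests on reading receipt of the device as having the implant in place, and on at least one implantation being attempted and abandoned. It does not touch the primary retear analysis.

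**What to change.** In Section 10.2, and in the SAP, define the device part of the safety set as every subject in whom REGENETEN implantation was attempted, meaning any component opened for or introduced into the subject, whether or not the implant stayed in place. State that these subjects appear in the device column of the adverse-event and device-deficiency tables. Report the numbers of attempted and completed implantations.

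The same sentence in Section 10.2, read literally, also leaves out the ARCR-alone arm. That is a separate matter, but the two are best settled in one rewrite. A set based on the study procedure having been started would bring in the abandoned cases too; the column they belong to would still have to be stated.

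The cost is wording. No extra patients are needed, and no extra CRF page, since Sections 9.1.3 and 12.3 already require the events to be recorded. The downside is that the reported device event figures may be slightly less favourable. If no implantation is abandoned, the change alters no reported figure.

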8.3.2 Secondary Endpoints

The secondary study endpoints are:

- The cumulative 3, 12, and 24 months retear rate after full-thickness ARCR augmented with REGENETEN (confirmed on MRI) versus ARCR alone;
- Overall performance of full-thickness ARCR augmented with REGENETEN versus ARCR alone at Baseline and at 3, 6, 12 and 24 months assessed by:
 - Oxford Shoulder Score (OSS),
 - Western Ontario Rotator Cuff (WORC)/Chinese version WORC (C-WORC) Index,
 - Constant-Murley Score,
 - Subjective shoulder value (SSV),
 - o EuroQol 5 Dimension 5 Level (EQ-5D-5L) Score,
 - Patient satisfaction Questionnaire,
 - Pain, Visual analog scale (VAS) Score (additionally at baseline, 2 weeks, 6 weeks, 3 months and 6 months);
- MRI Tendon Findings in ARCR augmented with REGENETEN versus ARCR alone postoperatively at Baseline, 3, 6, 12 and 24 months including:
 - Sugaya score,

CONFIDENTIAL AND PROPRIETARY

Study Protocol	Smith-Nephew
A Prospective, Multi-center, Randomized Controlled	Number:
Study to Evaluate the Safety and Efficacy of ARCR	REGENETEN.2020.01
augmented with REGENETEN™ Bioinductive Implant	Version: 2, 08 Dec 2021
System in Full-thickness Tears (large or massive) Repair versus ARCR alone	Page: 49 of 134

- Goutallier grading,
- o Total tendon thickness, tendon length,
- Size of retear (anteroposterior [AP]/mediolateral [ML]),
- Shape of retear;
- Outcome of Return to Work Questionnaire in ARCR augmented with REGENETEN versus ARCR alone (additionally at 2 and 6 weeks);
- Cumulative duration of opioid use in ARCR augmented with REGENETEN versus ARCR alone at 2 weeks postoperatively;
- Total operative time in ARCR augmented with REGENETEN versus ARCR alone;
- Sling type and mobilization time in ARCR augmented with REGENETEN versus ARCR alone.

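### Section 7.8.1 takes all data after a reoperation out of the study data, so the 12- and 24-month score comparisons omit post-reoperation values, and no rule says how they are handled

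*Combined protocol and SAP*

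**What the plan says.** Section 7.8.1 (Withdrawal from Treatment) introduces reoperation with the case where "the study device needs to be revised for any reason". It then covers who may join the revision repair group. Device-arm subjects may not. For the other arm: "However subjects that have been randomized into the ARCR alone arm can be enrolled into the Revision Repair subject group". The section closes with two sentences on what follows a reoperation: "Following reoperation subjects shall continue to have follow-up visits in order to monitor the subject's health status only", and "Potential data following the reoperation will not be included as study data but presented separately as safety data".

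Section 10.2 describes the FAS as "following the Intention to Treat principle including all randomized patients who were recruited into the study and attended at least one post-surgery assessment". It keeps patients in their randomised groups "regardless of the treatment they actually received, and regardless of subsequent withdrawal from treatment or deviation from the protocol".

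Section 8.3.2 lists the score endpoints under the line "Overall performance of full-thickness ARCR augmented with REGENETEN versus ARCR alone at Baseline and at 3, 6, 12 and 24 months assessed by": OSS, WORC/C-WORC, Constant-Murley, SSV, EQ-5D-5L, satisfaction and VAS pain. Return to work is a further secondary endpoint. Section 10.4.2 analyses the five main scores by visit, uses a repeated-measures ANCOVA for change from baseline, and uses a separate model for the comparison between groups at each time point. VAS pain is summarised with p-values. Satisfaction and return to work are summarised by response.

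No section says how a reoperated subject's later scores are to be treated. LOCF appears only in the abbreviation list.

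**The concern.** Reoperation happens after randomisation and is related to failure of the repair, which is what the implant is meant to reduce. If scores after that point are not study data, the 12- and 24-month group means (and earlier ones, after an early reoperation) describe only subjects who have not been reoperated by that visit. That group is partly selected by outcome, and the selection may differ between arms. The result is no longer the comparison that randomisation protects.

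At stake is the secondary objective of efficacy against ARCR alone. The primary 6-month retear endpoint is largely outside this point. It is cumulative, so a retear seen on MRI before reoperation still counts, although a reoperation with no earlier MRI retear could be lost.

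**Working it through.** **Setting the sections side by side**

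1. Section 7.8.1 is current text and its exclusion covers data in general, with no carve-out for scores.
2. Section 10.2 fixes which subjects are analysed and in which arm. It does not say which visits count. A reoperated subject therefore stays in the FAS and contributes visits up to the reoperation. What is lost is the later values.
3. Section 7.8.1 places this loss under withdrawal from treatment, an event that Section 10.2 says should not affect a patient's inclusion. The conflict is with the stated principle.
4. Sections 9.1.8 and 9.1.9 (12 and 24 months) list the questionnaires beside the reoperation form, with no exception for reoperated subjects. Collection is thus foreseen by one section, while another restricts the purpose of those visits to health status.

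**Size of the effect**

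The plan gives no reoperation rate and no score by reoperation status, so there is no figure to reproduce. All rates and deficits below are assumptions.

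Let p be the proportion reoperated before the visit, d the amount by which their later scores fall below those of the other subjects, and M the mean of subjects not reoperated.

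- Mean of all subjects in an arm: M - p × d. After exclusion: M. The arm mean rises by p × d.
- Change in the between-arm difference: (p_control - p_device) × d.

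| Control v device | Deficit d (OSS points) | Shift |
|---|---|---|
| any | 0 (revised shoulders recover fully) | 0 |
| equal rates | any | 0 |
| 5% v 2% | 5 | 0.03 × 5 = 0.15 |
| 12% v 4% | 10 | 0.08 × 10 = 0.8 |
| 15% v 5% | 15 | 0.10 × 15 = 1.5 |

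The rows pair low with low and high with high. The extreme corner, 15% v 2% with 15 points, gives 0.13 × 15 = 1.95.

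**Cross-check from the design rates**

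Section 11 assumes retear in 15% (device) and 30% (ARCR alone), with 130 per arm. Suppose 25% to 75% of retears are reoperated before the visit, with the same share in both arms (assumed).

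- Device: 0.25 × 15% = 3.75% to 0.75 × 15% = 11.25%, about 5 to 15 of 130.
- ARCR alone: 0.25 × 30% = 7.5% to 0.75 × 30% = 22.5%, about 10 to 29 of 130.
- The loss is 2:1 under the trial's own hypothesis.
- Shift with a deficit of 5 points and the low share: (0.075 - 0.0375) × 5 = 0.19.
- Shift with a deficit of 10 points and the high share: (0.225 - 0.1125) × 10 = 1.1.
- Shift with no deficit: 0.

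Both routes give a range from zero to somewhat over one point on a 48-point scale.

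**The case against.** The strongest reply is that cutting data at reoperation is a legitimate way to handle an intercurrent event. The subjects remain in the FAS, reoperation rate is reported as a separate endpoint (Sections 8.3.3 and 10.4.3), and the excluded data are presented as safety data, so failures are not concealed. Section 10 also calls itself brief and defers detail to the SAP. If the design hypothesis is right, the bias runs against the sponsor's device.

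Part of this stands. A reader might infer that Section 7.8.1 contradicts the FAS definition. It does not, because that definition selects subjects and not visits. The choice still has to be stated and justified as an analysis strategy, and here it appears only as a withdrawal rule. A later SAP rule cannot use scores that the protocol says are not study data, or scores never collected.

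Three other stronger readings are tempting:

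- *The rule applies to the device arm only, so benefit would be overstated.* The mention of the study device invites this. However, the next paragraph of Section 7.8.1 names ARCR-alone reoperations, and the exclusion sentence has no arm limit. The wording needs tidying, but a one-sided rule is not the natural reading.
- *Each arm loses its worst failures.* Reoperation also reflects surgeon and patient choice. Retears that are not reoperated stay in the comparison, and the documents give no scores by reoperation status.
- *The repeated-measures model recovers part of the loss.* Section 10.4.2 uses that model for change from baseline. The comparison between groups uses a separate model at each time point, with no stated use of earlier visits.

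The main-arm flowchart, which the amendment rationale says shows the process for reoperated patients, was not readable in the copy reviewed and could not be checked.

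**Conclusion.** The point holds for the secondary score endpoints. As written, the plan removes post-reoperation values from the 12- and 24-month comparisons of OSS, WORC, Constant-Murley, SSV, EQ-5D-5L and VAS pain, and from the summaries of satisfaction and return to work. This departs from the Intention to Treat principle in Section 10.2, and no other section says what happens to those values.

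The size depends on the between-arm difference in reoperation rate and on the score deficit after revision, neither of which the documents supply. Under the assumed paired ranges it is about 0 to 1.5 of 48 OSS points. The direction is not fixed: benefit is understated if the device lowers reoperations, and harm is masked if it raises them. The effect is modest and limited to secondary endpoints. It should be corrected while follow-up is running, because uncollected scores cannot be recovered.

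**What to change.** Replace the exclusion sentence in Section 7.8.1, and mirror it in the SAP, so that:

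- scheduled score assessments after a reoperation, timed from the index surgery, are collected in both arms and analysed in the randomised arm (FAS) with reoperation flagged;
- the rule is stated to apply to both arms, since the paragraph on reoperation opens with the study device;
- two sensitivity analyses are given: data cut at reoperation (the current rule), and the last score before reoperation carried forward to later visits;
- an ARCR-alone subject who enters the revision group still contributes index-timed visits to the randomised arm, with revision-group results reported separately.

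The cost is mainly protocol and SAP wording and completion of questionnaires at visits that already continue. Two items need care. Sections 9.1.8 and 9.1.9 do not list VAS pain at 12 and 24 months although Section 10.4.2 summarises it there, so those sections need aligning. Controls who enter the revision group will follow two clocks, because visits timed from revision need not coincide with visits timed from index surgery.

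The downside is that control scores after revision with REGENETEN carry some device effect. The sensitivity analyses show how much this matters.
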